9.2. Secondary Objectives

2. ACCEPTABILITY:

- a. To explore the acceptability of LA CAB+RPV amongst PLWH and health care workers delivering the regimen through a participant questionnaire, healthcare practitioner questionnaire and qualitative research.
- b. To compare patient-reported outcomes including quality of life, treatment satisfaction and treatment preference in those on LA CAB+RPV compared to those who remain on oral ART (demographically similar but not eligible for LA ART)

3. FEASIBILITY:

- c. To describe the feasibility of using the regimen from a clinical and patient perspective through outcomes in the participant and healthcare practitioner questionnaires
- d. To explore barriers and facilitators to effective implementation of the LA CAB+RPV regimen
- **4. FIDELITY:** To describe the fidelity of regimen delivery and associated monitoring compared to intended use in BHIVA guidelines

5. EFFECTIVENESS:

e. To characterise the UK-wide population who are switched to LA CAB+RPV and indications for switch

- f. To describe virological and clinical outcomes at one year of therapy in those on LA CAB+RPV and in those remaining on oral ART (demographically similar but not eligible for LA ART)
- g. To identify where actionable adjustments to implementation can be made to optimise overall adoption, sustainability and effectiveness of LA CAB+RPV

10. Outcome Measures

There are no interventional components to the study. Service-specific approaches to implementation of LA CAB+RPV in use at the study sites at study outset will be described, contrasted and compared.

Objective	Outcome measures	
Implementation outcomes		
ADOPTION 1. To quantify the adoption cascade	 a. Proportion of clinical cohort eligible for LA CAB+RPV according to BHIVA guidance b. Proportion of eligible adults offered/discussed a switch to LA CAB+RPV c. Proportion who accept the switch to LA CAB+RPV d. Proportion who remain on LA CAB+RPV at one year and reasons for switching off the regimen 	

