11.1.1. Observational study using routinely collected clinic data

The study will capture data from HIV-1 positive adults receiving long-acting cabotegravir and rilpivirine as part of their treatment regimen. All HIV-1 positive adults (≥ 16 years) who initiated long-acting cabotegravir and rilpivirine-based ART any time from 6 months prior to study site initiation will be eligible to be included in this study. A demographically similar comparator group on oral ART will also be invited to join the study. Routinely collected medical data from eligible and consenting participants' medical records will be extracted at key intervals, as laid out in the Schedule of Activities (see section 12.3.4), and entered into an electronic data capture system (Research Electronic Data Capture, REDCap). Variables of interest include demographic data, HIV treatment history, laboratory findings, which are all collected routinely in line with the BHIVA monitoring guidelines.

The total duration of patient follow-up is at least 1 year from the time of enrolment. The final analysis will be conducted following database lock after the last study participant has reached the 12 months treatment milestone and all data queries have been resolved.

Patients who received LA ART outside of the BHIVA criteria e.g. on compassionate grounds are of interest and can be included in the prospective study; the reasons for BHIVA criteria ineligibility and outcomes (duration of therapy, virological and clinical) will be described.

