11.1.5. Notes review to understand adoption cascade

A registry dataset of patients eligible for LA CAB/RPV will be generated from the main clinic database. Over the following 12 months, the clinic will then quantify the number of patients ever offered a switch to LA CAB+RPV, the number who accept the switch and the number who remain on the regimen for at least 1 year duration. Reasons for not being offered or declining a switch to LA CAB+RPV will be recorded.

[figure not shown]

Figure 2. Schematic of study including qualitative and quantitative aspects

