12.6. Registry dataset to quantify the adoption cascade

Participating clinics will be asked to perform a local database search and create a registry dataset of all participants eligible for the LA CAB+RPV regimen according to the BHIVA guidance, or who have already commenced the LA regimen. From this registry dataset, over the following 12 months, the clinic will then quantify the number ever offered a switch to LA CAB+RPV, the number who accept the switch and the number who remain on the regimen for at least 1 year duration. Reasons for not being offered or declining a switch to LA CAB+RPV will be recorded.

13. Risks and benefits for participants

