The number and proportion of participants who discontinue LA CAB+RPV and the reason for discontinuation will be described.

The 'end of study' is the point at which last participant final visit individual data has been entered into the electronic data capture system and all the qualitative work has been completed. Thereafter, the 'end of study' the close out visit will be performed. The study will only be considered 'closed' when all participants have completed their final study visit, all assessments completed, all the data have been entered into the database and all data queries resolved, close out visit conducted, the database locked and data analysis performed and reports written.

18. Study Management and Oversight

The study has undergone independent peer review at the Protocol Review Panel at University of Sussex.

The study will be managed via the Brighton and Sussex Medical School Department of Global Health and Infection at the University of Sussex. The study management group (SMG) consisting of the Chief Investigators, Co-Investigators, Study Manager, Data Manager will be responsible for the day-to-day conduct of the study and will troubleshoot any operational issues.

As this is a low-risk non-interventional protocol, there is no requirement for a data safety monitoring committee for this study. University of Sussex safeguarding policies will be followed https://www.sussex.ac.uk/safeguarding/.

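### The registry's single 12-month window cannot show one-year retention (primary outcome 1d) for anyone who accepts the switch after the registry is created

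*Protocol*

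**What the plan says.** Outcome 1d appears among the primary outcomes in the Protocol Summary (Section 6) and in the outcome table (Section 10): "Proportion who remain on LA CAB+RPV at one year and reasons for switching off the regimen". It is the last step of the adoption cascade.

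The component meant to quantify that cascade is the clinic registry. Section 12.6 says: "From this registry dataset, over the following 12 months, the clinic will then quantify the number ever offered a switch to LA CAB+RPV", and the same sentence goes on to "the number who accept the switch and the number who remain on the regimen for at least 1 year duration". Section 11.1.5 has the same arrangement: "Over the following 12 months, the clinic will then quantify the number of patients ever offered a switch to LA CAB+RPV". Besides eligible patients, the registry takes in those "or who have already commenced the LA regimen". On reasons, Section 12.6 states only: "Reasons for not being offered or declining a switch to LA CAB+RPV will be recorded".

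Two rules decide when data collection stops mattering. Section 11.1.1, which describes the cohort, says: "The final analysis will be conducted following database lock after the last study participant has reached the 12 months treatment milestone". Section 17 defines the end of study as the point when "last participant final visit individual data has been entered into the electronic data capture system" and the qualitative work is finished. Neither rule names the registry. Section 6 gives each site a total duration of 2 years.

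**The concern.** The observation window equals the length of time that has to be observed. Eligible people who are not yet on the regimen when the list is made have to be offered it, accept it, start it and then complete a year, all before the same 12 months run out. That is impossible for every one of them.

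At stake is the final step of a primary cascade. The earlier steps (eligible, offered, accepted) are clinic-wide counts. If the last step exists clinic-wide only for people who had started before the registry was made, the cascade does not follow the people who move through it during the study. An SAP cannot repair this: if sites make their last registry entry at month 12, the later status of new acceptors was never collected. The wording also leaves sites to choose their own reading, so figures from the planned 10–12 centres may not mean the same thing.

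A smaller gap sits beside it. Outcome 1d asks for reasons for switching off, but the registry lists only reasons for not being offered the switch or for declining it.

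**Working it through.** **Inputs from the protocol.** Registry window W = 12 months (11.1.5, 12.6). Retention requirement: at least 12 months on the regimen (12.6). Cohort enrolment of new switchers: 6–12 months after site initiation (11.2). Cohort follow-up: at least 12 months (11.1.1). Site duration: 24 months (Section 6). The protocol gives no expected retention or uptake pattern, so those below are assumptions.

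**1. The plan's own figure.** Enrolment plus follow-up is 6 + 12 = 18 months to 12 + 12 = 24 months. The upper end reproduces the 2-year site duration.

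**2. Observable time in the registry.** For acceptance at month t, with 0 < t ≤ 12, the longest observable time on treatment is W − t.

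- W = 12: 12 − t < 12 for every t > 0, so 0% can be seen to reach one year. This holds for any uptake pattern. With even uptake the median observable time is 6 months.
- W = 18: t ≤ 6 is required, so 6/12 = 50% with even uptake.
- W = 24: t ≤ 12 is required, so 100%, again for any uptake pattern.

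Borrowing the cohort's ±2-month visit tolerance (Table 1), so that 10 months would count, rescues only those with t ≤ 2. That is 2/12 = 16.7% with even uptake.

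**3. People who had already started.** Someone who started s months before day 0 has up to 12 + s months, so one year is observable. The overall registry count is therefore not zero.

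**4. What the registry would report for new acceptors (illustration).**

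- Literal reading: 0%.
- Counting those still on treatment at close: let R be true one-year retention, with constant hazard h = −ln(R)/12 and even uptake over 12 months. The expected proportion still on is (1 − e^(−12h))/(12h) = (1 − R)/(−ln R).
  - R = 0.90: 0.10/0.1054 = 0.949, so 5.1% appear to have stopped instead of 10%.
  - R = 0.80: 0.20/0.2231 = 0.896, so 10.4% appear to have stopped instead of 20%.
- Keeping new acceptors in the denominator, with only prior starters able to count as retained: the figure is R times the share who are prior starters. With R = 0.90 and shares of 25%, 50% and 75%, it reads 22.5%, 45% and 67.5%.

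The direction of the error depends on which reading a site adopts.

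**5. The triggers.** The final-analysis rule sits in the cohort section and refers to the last study participant. The end-of-study rule refers to a final visit. The only schedule of activities for patients (Table 1) is for those enrolled in the prospective cohort. Someone who accepts the switch but does not join the cohort has no scheduled final visit for either rule to wait for.

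**The case against.** The strongest reply is that 1d is not tied to the registry. The cohort follows new switchers for at least a year, has a month-12 data point, and Section 17 promises the number, proportion and reasons for discontinuing LA CAB+RPV. The final-analysis rule does wait for those people. The detailed primary objective in Section 9.1 lists only eligibility, discussion and acceptance, all of which a 12-month window can deliver. All of this stands. A reader might infer that 1d is zero or unusable for all new adopters, or that the triggers ignore new adopters altogether. The documents do not support either inference. What remains is that the cohort is a consented sample, that the protocol does not say it supplies 1d, and that Section 12.6 itself assigns a one-year retention count to the registry.

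Second, the registry includes people already on the regimen, so sites would not simply return zero. That is correct, and the point is confined to those who accept after day 0.

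Third, the 12 months could be meant to cover only offers and acceptances. The Gantt chart has a row for completing the registry, but its bars cannot be read in the text available, so the intended calendar cannot be checked. This is possible, but it is not what the sentence says, and no section states a later update. Section 12.6 does call registry patients participants, and Section 17 keeps the study open until all data are entered. Neither tells a site to go back for a status that the registry instructions do not request.

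Fourth, the 95% and 90% illustrations rest on assumed retention, constant hazard and even uptake. That is true, and they show direction and rough size only.

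**Conclusion.** The point holds as a defect in the registry wording. As written, 0% of people who accept after registry day 0 can be observed for one year. That follows from the window alone and needs no assumption. One-year retention is observable in the registry only for people who had already started, and elsewhere only for new switchers who consent to the cohort. Acceptors who are only in the registry are covered by neither closing trigger.

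Counting those still on treatment at close would overstate retention by about 5 percentage points at an assumed true 90%, and by about 10 at 80%. Those sizes depend on the assumptions above.

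The timetable is not at fault: 12 months of acceptances plus 12 months of follow-up equals the stated 2-year site duration. The correction is needed before registries close, because status that was not collected cannot be supplied by the analysis.

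**What to change.** In Sections 11.1.5 and 12.6, separate the two periods. Count offers and acceptances over the first 12 months after the registry is created. Then record each acceptor's status 12 months after their own switch, with the reason for any switch off the regimen. The registry then closes at about month 24.

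State in Section 10 whether the registry or the cohort supplies 1d. If both are to be reported, give each its own denominator.

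Add completion of registry follow-up to the final-analysis trigger in Section 11.1.1 and to the end-of-study definition in Section 17. The estimator and the handling of people who transfer out can be left to the SAP.

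The cost is one further registry update per site and a later cascade result. Month 24 fits the 2-year site duration only if the list is built at site opening. There is no slack, so a site that builds its list later would need its end date moved by the same amount.

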9.1. Primary Objective

1. ADOPTION: To describe the strategies being deployed in different UK HIV services to deliver LA CAB+RPV and to quantify the adoption cascade in terms of what proportion of each clinic cohort are: a) eligible for LA CAB+RPV in accordance with BHIVA

guidelines; b) have a switch to LA CAB+RPV discussed; c) accept a switch to LA CAB+RPV; and to ascertain reasons for attrition at each step of the cascade (Fig. 1).

[figure not shown]

Figure 1. Adoption cascade

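### The primary objective promises reasons for attrition at each cascade step, but the registry is not asked why people are ineligible and takes only a count of those still on treatment at one year

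*Protocol*

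**What the plan says.** Section 9.1 defines the cascade from the top of the clinic, asking "what proportion of each clinic cohort are: a) eligible for LA CAB+RPV in accordance with BHIVA" guidelines, then who has a switch discussed and who accepts it. It adds the aim "to ascertain reasons for attrition at each step of the cascade". Primary outcome 1d, in the section 10 outcome table and the protocol summary, reads "Proportion who remain on LA CAB+RPV at one year and reasons for switching off the regimen".

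Two sections describe the registry. Section 11.1.5 says: "A registry dataset of patients eligible for LA CAB/RPV will be generated from the main clinic database". Section 12.6 widens this slightly, to a "registry dataset of all participants eligible for the LA CAB+RPV regimen according to the BHIVA guidance, or who have already commenced the LA regimen". Both then ask the clinic to count those offered, those accepting and "the number who remain on the regimen for at least 1 year duration". Both end with the same sentence on reasons: "Reasons for not being offered or declining a switch to LA CAB+RPV will be recorded".

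Outside the registry, section 17 commits to describing why participants discontinue LA CAB+RPV. Section 11.1.1 commits to describing why patients in the prospective study who were treated outside the BHIVA criteria did not meet them.

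**The concern.** The objective and the data capture do not cover the same ground. A patient who fails a BHIVA criterion and has not started the regimen never enters the registry, so nothing about why that patient left the cascade is kept. This is the step with the whole clinic cohort as its denominator, and section 7 gives uncertainty about eligibility, and its possible variation by demographic group and setting, as a main reason for the study. An eligibility percentage alone does not show a commissioner whether people are excluded by resistance history, hepatitis B, BMI and subtype, or something else.

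At the other end, the registry counts those remaining on treatment but asks no reason of those who stopped. Any reasons come from a different and smaller group than the one behind the clinic-level proportion.

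**Working it through.** No arithmetic beyond counting applies, and the protocol gives no figure to reproduce. The check sets each cascade step against what the registry records, then against every other place where reasons are collected.

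**What the registry specifies, by step**

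1. Clinic cohort to eligible (9.1 item a, outcome 1a). Registry membership begins after this step, so ineligible patients who have not started are outside it. No reason is requested. Neither 11.1.5 nor 12.6 lists the size of the clinic cohort among the counts to return, although outcome 1a needs it as denominator.
2. Eligible to offered or discussed (item b, outcome 1b). Counted, with reasons recorded.
3. Offered to accepted (item c, outcome 1c). Counted, with reasons recorded.
4. Accepted to still on the regimen at one year (outcome 1d only; not listed in 9.1). Counted, with no reason requested.

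On the three steps named in 9.1, clinic-wide reasons are specified for 2 of 3, and the missing one is the first.

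**Whether another section fills step 1**

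- Section 11.1.1 covers reasons for ineligibility only in people who received LA ART outside the criteria and are in the prospective study. They are not the people whom ineligibility kept off the regimen.
- The oral ART comparators (11.2.1) are ineligible by definition. They are about 50 consented people, chosen to be demographically similar and matched where possible (sections 11.2.1 and 17). Their mix of reasons would not represent the ineligible part of each clinic, and section 12.3.2 does not list the reason for ineligibility as a data item.

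**Whether another section fills step 4**

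- Section 17 does, for cohort participants. The cohort requires individual consent (12.2) and is planned at about 10-20 LA patients per centre (11.2, which also gives 5-20). Reasons will therefore be described, but for a sample and not for every registry patient who stops.
- The protocol does not say whether the reasons in outcome 1d are meant to come from the registry or from the cohort.

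**Which criteria a search could tally**

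Section 7 lists nine BHIVA criteria. Three rest on judgement or patient attitude: significant need, ability to commit to two-monthly attendance, and acceptance of a small failure risk. On that reading, at most 9 - 3 = 6 could be settled by a database search, depending on what each clinic's database holds.

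**The case against.** Several points on the other side have force.

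- **Stopping.** A reader might infer that the study collects no reasons for discontinuation. The documents do not support that. Section 17 commits to describing them, and outcome 1d does not require them to be clinic-wide. A registry count combined with cohort reasons is a defensible mixed-methods split. What stands is that the protocol does not say this is the intended split.
- **Scoring.** Counting retention as a fourth step with no reasons at all would make coverage look worse than it is. Section 9.1 lists only three steps, and the cohort partly covers the fourth.
- **Missing fields.** The absence of a named stop date or stop reason in 12.3.2 and Table 1 does not show that these go uncollected. Section 16.2 leaves detail to an eCRF completion manual that is not shown.
- **Figure 1.** The phrase about each step is tied to a figure that is not shown, and outcome 1a is a bare proportion. It could be argued that ineligibility is a starting denominator and not attrition. The text of 9.1 nonetheless lists eligibility within the clinic cohort as the first item of the cascade and asks for reasons at each step.
- **Judgement-based criteria.** Patients who fail these may pass a database search and appear later as not offered or declined, where reasons are recorded. That narrows the gap at step 1 without closing it for the searchable criteria.
- **Local initiative.** Nothing stops a clinic from logging failed criteria during its search. Nothing asks it to either, so practice would differ between clinics.

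**Conclusion.** The concern holds for the first step. The primary objective asks for reasons that the registry, described the same way on this point in two sections, does not collect. This is a data-capture gap, so leaving the detail to a statistical analysis plan does not help. For retention the point is smaller: reasons are described, but only for the consented cohort, and the source for outcome 1d is unstated.

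The size is best put as coverage: clinic-wide reasons for 2 of the 3 steps in 9.1, with cohort-only reasons for the retention step added by outcome 1d. The number of people who leave at step 1 cannot be given, because the protocol states that the eligible proportion is unknown. The proportions in outcomes 1a to 1d are not biased by this gap. What is lost is the explanation attached to the first proportion and the clinic-wide basis for reasons attached to the last.

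The conclusion assumes that clinics follow 11.1.5 and 12.6 as written, and that Figure 1 does not redefine the steps listed in the text.

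**What to change.** In sections 11.1.5 and 12.6:

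- Ask each clinic to return its whole-cohort denominator and anonymous counts of patients failing each BHIVA criterion that its search can apply, and to state which criteria were applied. Note that criteria resting on judgement or patient attitude may surface later as not offered or declined.
- Add a stop date and a stop reason for every registry patient who discontinues.

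In section 10, state whether the reasons in outcome 1d come from the registry or the cohort.

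If the sponsor does not want the extra capture, narrow the wording on each step in 9.1 to the steps for which reasons are collected, and describe the reasons in 1d as those of the consented cohort.

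The cost is modest but not nil. Clinics already apply the criteria to build the registry and already follow registry patients for retention, so the additions are tallies and two fields per patient who stops. Tallying every failed criterion means checking each patient against each searchable criterion instead of filtering in sequence, and the counts will overlap and not sum to the number ineligible. Tallying only the first failed criterion is less work and does sum, but the result depends on the order of the filters, which would then have to be the same at every clinic.
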